5.3. Bosutinib Treatment Discontinuation

Patients meeting any of the following criteria should permanently discontinue bosutinib treatment:

1. Unsatisfactory Response (after dose escalation or with no option to dose escalate due to ongoing toxicities).
 - For CP 2nd-line patients, please refer to European LeukemiaNet (ELN) definition of Failure ([Appendix 5](#));
 - For CP 3rd or 4th-line patients, lack of CHR or lack of MCyR;
 - For AP and BP patients, lack of any hematologic response.
2. Disease Progression:
 - For CP, at least one of the following criteria:
 - Development of AP or BP CML;
 - Loss of CHR (in absence of cytogenetic response) confirmed by 2 complete blood counts (CBCs) at least 2 weeks apart; Loss of CHR is defined as:
 - WBC count that rises to $> 20.0 \times 10^9/L$;

- Platelet count that rises to $\geq 600 \times 10^9/L$;
- Appearance of extramedullary disease not present at baseline including hepatosplenomegaly by palpation or other extramedullary involvement proven by biopsy;
- Appearance of $\geq 5\%$ myelocytes + metamyelocytes in the peripheral blood or appearance of blasts or promyelocytes in the peripheral blood.
- Loss of MCyR (loss of CCyR or loss of PCyR);
- Increasing white blood count (WBC) in a patient without CHR, defined as doubling of WBC, to $> 20 \times 10^9/L$ on 2 occasions at least 2 weeks apart (after the first 4 weeks of treatment).
- For AP, at least one of the following criteria:
 - Development of confirmed BP;
 - Loss of previous hematologic response over a 2-week period;
 - Loss of CHR is defined as:
 - WBC count that rises to $> 20.0 \times 10^9/L$;
 - Platelet count that rises to $\geq 600 \times 10^9/L$;
 - Appearance of extramedullary disease not present at baseline including hepatosplenomegaly by palpation or other extramedullary involvement proven by biopsy;
 - Appearance of $\geq 5\%$ myelocytes + metamyelocytes in the peripheral blood or appearance of blasts or promyelocytes in the peripheral blood.
 - No decrease from baseline levels (if considered clinically relevant) in percentage blasts in peripheral blood or bone marrow on all assessments over a 4-week period.
- For BP (of any phenotype):
 - Increasing blasts (if considered clinically relevant) peripheral blood or bone marrow over a 4-week period;

3. Symptomatic Deterioration:

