7.1.1.1. Cytogenetic Response Assessment

Cytogenetic analysis will be performed by conventional cytogenetics from bone marrow, requiring at least 20 metaphases in order to evaluate number of Ph+ cells to determine cytogenetic response. Conventional cytogenetic assessment will be performed at scheduled visits until MMR is observed.

Only chromosome banding analysis of marrow cell metaphases will be used to assess the degree of CyR. Upon achieving CCyR by the conventional cytogenetic assessment, FISH of blood interphase nuclei with an appropriate probe (Dual-Color Dual-Fusion or Dual-Fusion FISH) could substitute for chromosome banding analysis of marrow cell metaphases for the assessment of maintenance of the CCyR (which is then defined by <1% BCR-ABL1-positive nuclei of at least 200 nuclei) until MMR is reached. Loss of CCyR using FISH will require resumption of bone marrow conventional cytogenetic assessment (unless the CML disease status is proven to be MMR by qRT-PCR).

For Ph- CML patients, conventional cytogenetic analysis will be performed only at screening and at the time of suspected progression and/or failure. Conventional cytogenetic assessment will be used to detect other potential cytogenetic abnormalities and molecular cytogenetic assessment (FISH) will be used to detect cryptic/variant translocations. Cytogenetic analysis will be conducted locally. Note: The cytogenetic assessment needs to be repeated at least 28 days later to confirm CCyR CML disease status for Ph+ CML patients (when the cytogenetic response is first observed in the absence of MMR, e.g. once CCyR is achieved by G-banding,

FISH is needed to confirm the achievement/maintenance of CCyR at least 28 days later). Loss of cytogenetic response must be confirmed by 2 assessments at least 4 weeks apart. (Note: if confirmation is lacking and the patient goes off treatment due to progressive disease, the assumption is that loss of cytogenetic response (CyR) is confirmed for this study; therefore, the confirmation of loss of CyR 4 weeks apart is not required in this clinical context).

Karyotypic abnormalities in Ph- subclones should be recorded. See [Appendix 11](#) for CyR criteria definitions.

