Cumulative response is any response on-treatment. Landmark “at” responses need to occur within a 2 week window of the landmark for those before Week 39 and within a 4 week window for Week 39 and after (eg, Month 3 is \geq Week 11 to \leq Week 15, Month 18 is \geq Week 74 to \leq Week 82, etc.). Molecular responses are defined in [Appendix 2](#). Response is unconfirmed for cytogenetic and molecular and confirmed for hematologic with 2 consecutive responses at least 28 days apart. The date of hematologic confirmed response is the date of the first response. To be considered a responder, the patient must have maintenance of baseline response while on-treatment or an improvement from baseline. The hierarchy to assess for best response from best to worst is \geq 4.5-log reduction of BCR-ABL transcripts from standardized baseline on the international scale (MR^{4.5}), MR⁴ (\geq 4-log reduction), MMR (\geq 3-log reduction, same as MR³), CCyR, PCyR, CHR, and OHR.

Duration of response (DOR) for CCyR and MMR, is defined as the time from first response to confirmed loss, progression of disease as assessed by the investigator, or on-treatment death due to any cause ([date of loss – date of first response + 1]/30.4). For CCyR, confirmed loss is defined as 2 consecutive assessments with >0 Ph+ metaphases at least 28 days apart. For MMR, confirmed loss is defined as 2 consecutive assessments at least 28 days apart with a <3 -log ($>0.1\%$) reduction in transcripts from standardized baseline one of which corresponds to a \leq 2-log reduction ($\geq 1\%$). The date of confirmed loss is the earlier of first loss, progression, or death date. Patients without confirmed loss, progression, or death are censored at the last valid assessment where response could be assessed.

Exploratory

- *PFS.*
- *OS.*
- *Presence of BCR-ABL mutations.*
- *For Ph- CML patients, cumulative best response (OHR and MMR) anytime on treatment.*
- *Patient reported outcome (PRO) endpoints as measured by Functional Assessment of Cancer Therapy-Leukemia (FACT-Leu).*
- *To collect banked biospecimens for exploratory research, unless prohibited by local regulations or ethics committee decision. Collection of banked biospecimens unless prohibited by local regulations or ethics committee decision. Additional information on collection and potential use is provided in the Banked Biospecimens section.*

- Time to MMR, MR⁴, MR^{4.5}, CCyR, and MCyR.
- Duration of MR⁴ and MCyR.

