8.2.3. Analysis of Exploratory Efficacy Endpoints

The time to molecular and cytogenetic response analyses are based on the evaluable analysis set. Cumulative incidence of response adjusting for the competing risk of treatment discontinuation due to any reason without response, as described in [Section 8.1](#), will be used. The percentage of responders without treatment discontinuation and the percentage of treatment discontinuation without response will be summarized.

The duration of cytogenetic and molecular response exploratory analyses follow the same rules as the secondary DOR analyses except the percentages of MCyR, CCyR, and PCyR and MR⁴ will be summarized.

The time to transformation analysis is based on the full analysis set. Cumulative incidence of transformation adjusting for the competing risk of treatment discontinuation due to any reason without transformation, as described in [Section 8.1](#), will be used. The percentage of transformation without treatment discontinuation and the percentage of treatment discontinuation without transformation will be summarized. The specific disease stage transformation (accelerated or blast phases) will also be listed.

The PFS analysis is based on the full analysis set. The K-M method, with or without insufficient clinical response as assessed by the investigator as an event or cumulative incidence of on-treatment progression or death adjusting for the competing risk of treatment discontinuation without the event, as described in [Section 8.1](#), will be used.

The OS analysis is based on the full analysis set. The K-M method, as described in [Section 8.1](#), will be used. The number of deaths and causes of death will be summarized. Time on study from date of first dose to date of last contact and reasons for discontinuing participation will also be summarized.

The percentage of patients with baseline and emergent mutations, along with the specific types of mutations, will be summarized. The percentage of patients with cumulative MCyR, CHR, MMR, and OHR (AP and BP patients only) by baseline mutation status will be provided. The distributions of PFS and OS will also be displayed for patients with a baseline mutation versus those assessed but without a baseline mutation.

The percentage of Ph- CML patients in each best response category will be summarized.

Missing values and incomplete data will be handled as described in [Section 7](#) of this analysis plan.

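### In CP second-line patients, the recorded stop reason decides whether a single unconfirmed loss of CCyR is a duration-of-CCyR event or is censored at the assessment that shows the loss

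*SAP*

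**What the plan says.** **Events and censoring.** SAP 6.1 (Secondary) runs duration of response for CCyR and MMR from first response to "confirmed loss, progression of disease as assessed by the investigator, or on-treatment death due to any cause". A single loss is not enough: "For CCyR, confirmed loss is defined as 2 consecutive assessments with >0 Ph+ metaphases at least 28 days apart". Dating follows the rule "The date of confirmed loss is the earlier of first loss, progression, or death date". For everyone else, "Patients without confirmed loss, progression, or death are censored at the last valid assessment where response could be assessed". Protocol 9.2.2 likewise counts a treatment stop as an event only when disease progression is the cause.

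**Stop reasons.** Protocol 5.3 has two separate entries that cover loss of CCyR in a CP second-line patient.
- Under Unsatisfactory Response: "For CP 2nd-line patients, please refer to European LeukemiaNet (ELN) definition of Failure". Both Failure tables in Appendix 5 list loss of CCyR at any time.
- Under Disease Progression for CP: "Loss of MCyR (loss of CCyR or loss of PCyR".

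**Confirmation.** Protocol 7.1.1.1 states "Loss of cytogenetic response must be confirmed by 2 assessments at least 4 weeks apart". It waives this only when the patient leaves treatment for progressive disease.

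**PFS by contrast.** SAP 8.2.3 plans the Kaplan-Meier analysis of PFS "with or without insufficient clinical response as assessed by the investigator as an event". SAP 8.2.2 has no counterpart for duration of response.

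**The concern.** The same laboratory finding can meet either stop reason, and no section says which one governs. The analysis nevertheless treats the two reasons in opposite ways. If the site records progression, the response ends at the loss. If it records unsatisfactory response and no confirming sample exists, the patient leaves the risk set on that same date as if still in response. A stop for toxicity or withdrawal straight after a single loss has the same effect in any line of therapy.

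Censoring at the moment of an observed loss is informative: these patients leave the risk set because of the outcome being measured. The bias in retained response is upward. If cumulative incidence is used in place of Kaplan-Meier, the loss becomes a competing discontinuation and the incidence of loss is understated.

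Duration of CCyR is a named secondary endpoint in an open-label, single-arm study that supports conversion of a conditional authorisation. The primary response endpoints are not affected.

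**Working it through.** The plan states no figure to reproduce here. The check applies the SAP rule to one patient, asks whether a confirming sample is assured, and then illustrates the effect on Kaplan-Meier.

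**1. One patient, two recorded reasons (dates assumed).** First CCyR is at Week 26 (day 26 × 7 = 182) and a single loss at Week 78 (day 78 × 7 = 546). Treatment then stops. SAP formula: (date − date of first response + 1)/30.4.

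| Later marrow showing loss | Recorded as progression | Recorded as unsatisfactory response |
|---|---|---|
| None | Event, (546 − 182 + 1)/30.4 = 12.01 months | Censored, 12.01 months |
| 21 days later | Event, 12.01 months | Censored, (567 − 182 + 1)/30.4 = 12.70 months |
| 35 days later | Event, 12.01 months | Event, 12.01 months |

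Without a confirming sample at least 28 days later, only the recorded reason separates an event from a censored time.

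**2. Is a confirming sample assured?**
- SAP 6 counts an evaluation as on-treatment up to 28 days after last dose. The confirmation interval of at least 28 days runs from the loss sample. If dosing continues for d days after that sample, and the confirming sample must itself be on-treatment, it has to fall between day 28 and day 28 + d. For d = 7 that is days 28 to 35, and for d = 14 it is days 28 to 42. So confirmation is possible.
- Protocol 6.3 requires an End of Treatment marrow when the stop is for progression or failure, but waives procedures already collected in the previous 6 weeks (42 days). When d is 14 or less, 28 + d is at most 42, so the loss sample can itself satisfy the visit and no second marrow need be taken.
- For a stop due to toxicity or withdrawal, Protocol 6.3 requires no marrow at all.
- After Week 52, scheduled assessments are 26 weeks apart (Weeks 78, 104, 130, 156 and 182), so a second scheduled sample within the window is unlikely.

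**3. Illustrative effect on Kaplan-Meier.** The documents give no number of CCyR responders or losses, so all counts are assumed. Take 10 losses at distinct times and no other censoring before the last of them. Of these, k are recorded so that they are censored at the loss, spread through the sequence.

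With 30 responders and all 10 counted, retention is 20/30 = 66.7%. With every second loss censored, starting with the first, the events occur with 29, 27, 25, 23 and 21 at risk:

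(28/29)(26/27)(24/25)(22/23)(20/21) = 81.3%.

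| Responders | k = 0 | k = 2 | k = 5 | k = 10 |
|---|---|---|---|---|
| 30 | 66.7% | 71.8% | 81.3% | 100% |
| 60 | 83.3% | 86.3% | 91.2% | 100% |

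The direction is upward in every case. The size depends on k, which is unknown.

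**The case against.** **Loss of CCyR is progression by definition, so the recorded reason should not matter.** The progression list in SAP 6.1 does include it. But that list is given for PFS, where progression must also be the discontinuation reason on the CRF. For duration of response the SAP relies on progression as the investigator assesses it, and SAP 8.2.3 treats insufficient clinical response as something other than progression. The text therefore leaves the site's classification in control.

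**The affected group is narrow.** This stands in part. Unsatisfactory Response applies only once dose escalation has been tried or is ruled out by toxicity. A patient who is escalated stays under observation, which makes a second assessment likely. The double listing is confined to CP second line, because for third and fourth line the criterion is lack of CHR or MCyR. SAP 8.2.2 reports CP as a whole, which dilutes the effect.

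**The plan already limits the damage.** Kaplan-Meier is used only if most responders stay on treatment until progression or loss. Reasons for failure are summarised, efficacy data are listed, and there are no hypotheses or decision rules. This makes the problem visible to a careful reader but does not correct the estimate.

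**Stronger readings that the documents do not support.**
- A reader might infer that a loss first seen at the last visit can hardly ever be confirmed. That treats the two 28-day periods as starting together. One runs from the loss sample and the other from last dose, and an End of Treatment marrow is required for failure unless waived.
- A reader might extend the double listing to MMR. Loss of MMR is not a CP progression criterion in Protocol 5.3, and both Appendix 5 tables tie it to two consecutive tests with one at 1% or more.

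**Conclusion.** The point holds for duration of CCyR. A single loss without a confirming assessment is an event when the stop is recorded as progression and is censored at the loss otherwise. For CP second-line patients the protocol allows either record for the same finding. The bias is upward.

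Its size cannot be determined from the documents. The rise from 66.7% to 81.3% rests on assumed counts (30 responders, 10 losses, 5 of them censored at the loss) and is an illustration, not an estimate. A reader might take it as the expected error, but nothing in the documents fixes how many losses are both unconfirmed and recorded under a reason other than progression. The conclusion also assumes that the site's classification determines what counts as investigator-assessed progression.

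This is a secondary, descriptive endpoint. The change is worth making because it is cheap and the PFS analysis already allows for the same ambiguity.

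**What to change.** 1. **SAP 6.1, CCyR.** If the last on-treatment cytogenetic assessment before permanent discontinuation shows loss, and no later on-treatment assessment shows response, count a loss dated at that assessment whatever the recorded stop reason. Keep two-assessment confirmation for patients who continue treatment.
2. **SAP 8.2.2.** Add a sensitivity version of duration of response that counts discontinuation for insufficient clinical response as an event, matching the version planned for PFS.
3. **MMR.** Keep the existing loss definition, including the requirement that one of the two values be at least 1%. Do not count a single value above 0.1% as loss: that would contradict Protocol 7.1.1.4 and SAP 6.1, and could turn one marginal reading before a toxicity stop into a failure. Use only the sensitivity version in item 2.
4. **Protocol.** Sections 5.3 and 7.1.1.1 and Appendix 5 must be reconciled on which stop reason covers loss of CCyR and whether that loss must be confirmed. No clinical rule is proposed here.

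The cost is SAP wording and one extra table, with no new data. Reported durations of CCyR would become somewhat shorter, and some terminal unconfirmed losses counted under item 1 may be false.

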Efficacy and safety data from the Phase 1/2 study, Study 200, and the Phase 3 study, Study 3000, are presented below according to phase of disease and line of therapy, as of 28 March 2011 for efficacy and 15 February 2012 for safety (Study 200) and as of 26 September 2011 (Study 3000). Pooled safety data from Study 200, Study 3000, and the Phase 1/2 Japanese study, Study 2203, are presented below as of 15 November 2010. The most current safety data are contained in the Investigator's Brochure.

Second-Line CP CML

A total of 288 CP CML patients were enrolled and treated in the second-line setting in Study 200. The primary population for the efficacy response analyses was the evaluable population for imatinib-resistant patients, which included all treated patients with an adequate baseline assessment for the respective endpoint. The major cytogenetic response (MCyR) rate at Week 24 in the primary cohort (imatinib-resistant second-line CP CML) for the evaluable population (n=186) was 35.5%, with 24.2% attaining complete cytogenetic response (CCyR). Cumulative MCyR (defined as any on-treatment MCyR response during that period) was achieved in 55.4% of patients, with 43.0% attaining a CCyR. Cumulative MCyR and CCyR were newly achieved or maintained from baseline in 58% and 46% of patients, respectively. For patients with imatinib-intolerant CP CML, the MCyR rate at Week 24 in the evaluable population (n=80) was 30.0%, with a 25% CCyR rate at Week 24. Cumulative MCyR was achieved in 48.8% of patients, with 42.5% attaining a CCyR. Cumulative MCyR and CCyR were newly achieved or maintained from baseline in 61% and 54% of patients, respectively.

In the evaluable population of second-line CP CML (n=287), 85.0% achieved cumulative CHR, a secondary endpoint defined as a confirmed CHR or maintenance of baseline CHR during treatment with bosutinib. Of the 141 patients who did not have a CHR at baseline, 77.3% achieved a confirmed CHR. The Kaplan-Meier (K-M) estimates of PFS for the CP CML second-line all-treated population (n=288) were 91.3% and 80.6% at Year 1 and Year 2, respectively; the K-M median PFS has not been reached. The K-M estimates of overall survival (OS) were 96.8% and 90.6% at Years 1 and 2, respectively; the K-M median OS has yet to be reached.

Third-Line CP CML

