9.2.2. Analysis of Secondary Endpoints

Percentages for the following secondary endpoints will be calculated:

- Cumulative MCyR anytime on treatment in the CP, AP and BP Ph+ CML patient populations.
- Cumulative confirmed OHR anytime on treatment in the different advanced phase (AP, BP) Ph+ CML patient populations by lines of prior of therapy.
- Cumulative best response anytime on treatment in the different CP, AP, and BP Ph+ CML patient populations, also in the 4th- or later-line treatment setting. The hierarchy to assess for best response is MR4.5, MR4, MMR, CCyR, PCyR, CHR, and OHR.
- Landmark MCyR at 3, 6, 12, 18, and 24 months in the different CP, AP and BP Ph+ CML patient populations.
- Landmark confirmed OHR at 3, 6, 9, 12, 18, and 24 months in the AP and BP Ph+ CML patient populations.
- Cumulative confirmed CHR anytime on treatment in the CP, AP and BP Ph+ CML patient populations.
- Cumulative MMR anytime on treatment in the CP, AP and BP Ph+ CML patient populations.
- Duration of CCyR.
- Duration of MMR.

Analyses of hematologic and cytogenetic response will be based on the data from the local laboratory assessment. Analyses of molecular response will use the data from the independent central laboratory.

Duration of response is defined as the interval from the date of first on-treatment response to the date of confirmed loss of response, death within 28 days of last dose, or treatment discontinuation due to disease progression. Responders without loss of response will be censored at the last valid assessment for the respective endpoint.

The secondary time-to-event endpoint duration of response will be summarized using the Kaplan-Meier method or by cumulative incidence, whichever is more appropriate, depending on the competing risks (e.g., treatment discontinuation without disease progression in the analysis).

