6.1. Efficacy Endpoint(s)

Primary

- *Cumulative confirmed MCyR defined as Complete Cytogenetic Response (CCyR) or Partial Cytogenetic Response (PCyR) by 1 year (52 weeks) in 2nd and 3rd line CP patients.*
- *Cumulative confirmed MCyR by 1 year (52 weeks) in 4th and later line CP patients.*
- *Cumulative confirmed OHR defined as Complete Hematological Response (CHR) or Return to Chronic Phase (RCP) by 1 year (52 weeks) in AP and BP patients.*

The local cytogenetic assessments will be used for the primary endpoint analysis in CP patients. The local hematologic assessments will be used for the primary endpoint analysis in AP and BP patients.

Cumulative response is any response on-treatment up through Week 52 (based on the date of assessment) with a 4 week window (\leq Week 56). Response is confirmed for cytogenetic and hematologic with 2 consecutive responses at least 28 days apart. The date of confirmed response is the date of the first response. Cytogenetic and hematologic responses are defined in [Appendix 2](#) and [Appendix 1](#). MCyR is defined as a CCyR or PCyR. OHR is defined as CHR or RCP. To be considered a responder, the patient must have maintenance of baseline response for \geq 5 weeks for hematologic response or \geq 52 weeks for cytogenetic response or an improvement from baseline. Patients with PCyR at baseline must attain CCyR on-treatment to be counted as a cytogenetic responder. Patients with at least MMR and a deeper molecular response than baseline are counted as confirmed CCyR.

Secondary

- *Cumulative MCyR in CP, AP and BP patients.*
- *Cumulative confirmed OHR in AP and BP patients by line of therapy.*
- *Cumulative best response in CP, AP, and BP patients.*
- *MCyR at 3, 6, 12, 18, and 24 months in CP, AP, and BP patients.*
- *Confirmed OHR at 3, 6, 9, 12, 18, and 24 months in AP and BP patients.*
- *Cumulative confirmed CHR.*
- *Cumulative MMR in CP, AP, and BP patients.*
- *Duration of CCyR.*
- *Duration of MMR.*

The local cytogenetic assessments will be used for the secondary endpoint analyses for all patients. The local hematologic assessments will be used for the secondary endpoint analyses for all patients. *Molecular assessments will be performed at a central laboratory. Endpoint analysis for molecular response will be carried out by independent central analysis.*

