- Time to confirmed transformation on-treatment.

The local cytogenetic assessments will be used for the exploratory endpoint analyses for all patients. The local hematologic assessments will be used for the exploratory endpoint analyses for all patients. *Molecular assessments will be performed at a central laboratory. Endpoint analysis for molecular response will be carried out by independent central analysis.*

Time to response is the time from first dose to first response, unconfirmed for molecular and cytogenetic ([date of first response – first dose date +1]/30.4). Patients without events are censored at the last molecular or cytogenetic assessment where response could be assessed for the respective endpoint.

DOR for MCyR follows the same rules as the secondary endpoint of DOR for CCyR. DOR for MR follows the same rules as the secondary endpoint of DOR for MMR except confirmed loss is defined as 2 consecutive assessments at least 28 days apart with a <4-log (>0.01%) reduction in transcripts from standardized baseline one of which corresponds to a \leq 3-log reduction (\geq 0.1%).

PFS is defined as the time from first dose to objective progression or relapse as assessed by the investigator and noted as the reason for permanent treatment discontinuation on the case report form (CRF) or on-treatment death due to any cause ([date of progression – first dose date +1]/30.4). Patients without events are censored at the last cytogenetic, hematologic, or laboratory assessment where progression could be assessed. Progression is defined as:

- *For CP, at least one of the following criteria:*
 - *Development of AP or BP CML;*
 - *Loss of CHR (in absence of cytogenetic response) confirmed by 2 complete blood counts (CBC) at least 2 weeks apart; Loss of CHR is defined as:*
 - *WBC count that rises to $>20.0 \times 10^9/L$;*
 - *Platelet count that rises to $\geq 600 \times 10^9/L$;*
 - *Appearance of extramedullary disease not present at baseline including hepatosplenomegaly by palpation or other extramedullary involvement proven by biopsy;*
 - *Appearance of $\geq 5\%$ myelocytes + metamyelocytes in the peripheral blood or appearance of blasts or promyelocytes in the peripheral blood;*
 - *Loss of MCyR (loss of CCyR or loss of PCyR);*

- *Increasing white blood count (WBC) in a patient without CHR, defined as doubling of WBC, to $>20 \times 10^9/L$ on 2 occasions at least 2 weeks apart (after the first 4 weeks of treatment).*

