Appendix 2. DEFINITIONS OF HEMATOLOGIC, CYTOGENETIC, AND MOLECULAR RESPONSE

Response by Type	Definitions
Hematologic Complete (CHR)	WBC <10 x 10⁹/L Peripheral Blood Basophils <5% No Peripheral Blood myelocytes, promyelocytes, myeloblasts in the differential Platelet count <450 x 10⁹/L Spleen nonpalpable
Cytogenetic * Complete (CCyR) Partial (PCyR) Minor (mCyR) Minimal (minCyR) None (noCyR)	No Ph+ metaphases 1% to 35% Ph+ metaphases 36% to 65% Ph+ metaphases 66% to 95% Ph+ metaphases >95% Ph+ metaphases
Molecular Deep Molecular Response (MR4, MR4.5)	MR4= either (i) detectable disease with <0.01% BCR-ABL1^{IS} or (ii) undetectable disease in cDNA with >10 000 ABL1 transcripts MR4.5 =either (i) detectable disease with < 0.0032% BCR-ABL1^{IS} or (ii) undetectable disease in cDNA with >32,000 ABL1 transcripts in the same volume of cDNA used to test for BCR-ABL1. Ratio of BCR-ABL^{IS} ≤0.1%**.
Major (MMR)	

Abbreviations: CHR, complete hematologic response; CCyR, complete cytogenetic response, PCyR, partial cytogenetic response; Ph+, Philadelphia Chromosome positive; MCyR, major cytogenetic response; mCyR, minor cytogenetic response; minCyR, minimal cytogenetic response; noCyR, no cytogenetic response; MR4, MR4.5, deep molecular response; MMR, major molecular response.

*If bone marrow metaphases cannot be obtained or evaluated by chromosome banding analysis, the definition of CCyR (defined as <1% for FISH) may be based on interphase FISH of blood cells, provided that it is performed with Dual-Color Dual-Fusion or Dual-Fusion FISH probes and at least 200 nuclei are scored.

PCyR and CCyR are counted together and reported as MCyR.

**With ≥5,000 ABL1 transcripts.

Definitions of Hematologic Response for AP and BP CML*

CHR**	WBC \leq institutional upper limit of normal (ULN) ANC \geq 1.0 x 10⁹/L Platelet count \geq 100 x 10⁹/L BM Blasts \leq 5%*** No peripheral blood blasts or promyelocytes; Peripheral blood myelocytes + metamyelocytes $<$ 5%; Basophils in peripheral blood $<$ 5%* No evidence of extramedullary involvement
--------------	---

*The maximum % of basophils in peripheral blood was modified from <2 to $<5\%$ for a less restrictive constraint and alignment with the CHR criteria for CP CML patients according to ELN guidelines.

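### Read literally, the SAP's exploratory duration of MCyR uses the CCyR loss rule (>0 Ph+ metaphases), so repeated PCyR assessments after first response are recorded as loss of MCyR

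*SAP*

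**What the plan says.** Duration of MCyR appears among the exploratory endpoints in SAP 6.1; it is not in the endpoint table of Protocol Section 2. Its definition is a single sentence: "DOR for MCyR follows the same rules as the secondary endpoint of DOR for CCyR".

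The rule it points to is in the secondary part of SAP 6.1: "For CCyR, confirmed loss is defined as 2 consecutive assessments with >0 Ph+ metaphases at least 28 days apart". Loss is dated at the first of the qualifying assessments, or at progression or death if earlier. Patients without any of these are censored at the last valid assessment.

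On what MCyR is, SAP 6.1 says "MCyR is defined as a CCyR or PCyR", and the footnote to SAP Appendix 2 says "PCyR and CCyR are counted together and reported as MCyR". Appendix 2 sets CCyR at no Ph+ metaphases and PCyR at 1% to 35%.

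The sentence that follows the MCyR rule shows how the SAP changes a loss threshold when it means to: "DOR for MR follows the same rules as the secondary endpoint of DOR for MMR except confirmed loss is defined as", after which new transcript cut-offs are given. SAP 8.2.3 says that the duration "exploratory analyses follow the same rules as the secondary DOR analyses except the percentages of MCyR, CCyR, and PCyR" (and MR4) will be summarised. That exception concerns only which percentages are reported.

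**The concern.** The >0 threshold is the exact complement of CCyR, so it suits duration of CCyR. It is not the complement of MCyR, because every PCyR assessment is above 0% Ph+. Carried over unchanged, the rule makes the same laboratory result both the response and its loss.

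The error has a known direction. Patients who hold PCyR get an early event where they should be censored or have a later event, so the Kaplan-Meier duration is too short, or the cumulative incidence of loss too high. The SAP's outputs would also disagree. A patient who was not in PCyR at baseline and holds PCyR from Week 13 to Week 104 is an MCyR responder at the 3, 6, 12, 18 and 24 month landmarks, yet the duration table would show MCyR lost at Week 26.

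**Working it through.** The documents give no figure for this endpoint, so there is nothing to reproduce. The check applies the SAP rule to example patients.

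**Inputs.**
- Formula (SAP 6.1): duration = (date of loss or censoring − date of first response + 1)/30.4 months.
- Visits (Protocol 6.2): Weeks 13, 26, 39, 52, 78, 104, and so on. Every gap exceeds 28 days.
- Written loss threshold: >0% Ph+. Threshold consistent with MCyR (Appendix 2): >35% Ph+.
- Loss is counted from the first assessment after the response visit.

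**Results in months.**

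| Patient | Rule >0% | Rule >35% |
|---|---|---|
| PCyR stable, Weeks 13 to 104 | loss at Week 26: (91+1)/30.4 = 3.03 | censored at Week 104: (637+1)/30.4 = 20.99 |
| PCyR at Weeks 13, 26 and 39, then CCyR to Week 104 | loss at Week 26: 3.03 | censored at Week 104: 20.99 |
| PCyR at Weeks 13 and 26, then 60% Ph+ from Week 39 | loss at Week 26: 3.03 | loss at Week 39: (182+1)/30.4 = 6.02 |
| PCyR at Week 13, CCyR at the next visit and kept to Week 104 | censored: 20.99 | censored: 20.99 |

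In the second row the response deepens and is still recorded as lost. In the third row the loss is real but is dated 13 weeks early.

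**Variations on the first row.** If first response is at Week 52, the next visit is Week 78 and the recorded duration is (182+1)/30.4 = 6.02. If the response visit could itself count as the first loss, it would be 1/30.4 = 0.03; the SAP does not say so, and the 3.03 figure does not rely on it.

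**Time on treatment.** The 20.99-month case needs a patient who stays on treatment in PCyR. Protocol 5.3 lists lack of MCyR, not PCyR, as unsatisfactory response for third- and fourth-line CP patients. For second-line patients switched for intolerance, Protocol Appendix 5 classes any Ph+ metaphases at Month 12 as failure. If such a patient's last assessment is at Week 52 and no progression is recorded, the contrast is 3.03 against (273+1)/30.4 = 9.01.

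**Context on how common PCyR is.** Protocol 1.2.2 reports for the earlier study's imatinib-resistant second-line CP cohort: "Cumulative MCyR and CCyR were newly achieved or maintained from baseline in 58% and 46% of patients, respectively". The corresponding figures for the imatinib-intolerant cohort are 61% and 54%. PCyR as best cytogenetic response, as a share of MCyR responders:
- newly achieved or maintained: (58−46)/58 = 20.7% resistant; (61−54)/61 = 11.5% intolerant;
- newly achieved only: (55.4−43.0)/55.4 = 22.4% resistant; (48.8−42.5)/48.8 = 12.9% intolerant.

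These are differences of reported percentages, not patient counts.

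**The case against.** The strongest reply is that carrying over the rules means carrying over only the framework: start date, confirmation interval, progression, death and censoring, with loss understood as loss of the response in question. Several passages support this. The threshold sentence is expressly limited to CCyR. Protocol 7.1.1.1 has a general requirement that loss of cytogenetic response be confirmed at least 4 weeks apart. Protocol 9.2.2 is also general: "Duration of response is defined as the interval from the date of first on-treatment response to the date of confirmed loss of response". The CP progression list treats loss of MCyR as loss of either CCyR or PCyR, and a patient who stays in PCyR has lost neither. Authors who list PCyR among the responses summarised are unlikely to have meant it as a loss. The exception for the deeper molecular response may be there only because its two numerical tiers had to be spelled out.

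What stands is that this reading is possible and may be what was intended. It is not stated. No passage gives a loss level for duration of MCyR, and the adjacent sentence does write an exception to confirmed loss where the threshold differs. If the framework reading was meant, the level is missing and the same sentence is needed.

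The objection on importance also has force. The endpoint is exploratory and found only in the SAP, in a descriptive study with no hypotheses or decision rules (SAP 4.1 and 4.2).

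**Conclusion.** As written, the rule records loss of MCyR in patients who still meet the SAP's definition of MCyR, and it biases the exploratory duration short. For an individual patient the difference can be 3.03 against 20.99 months, assuming scheduled visits and PCyR held from Week 13 to Week 104.

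Three stronger conclusions are tempting and are not supported.
- A reader might infer that 11% to 22% of MCyR responders are affected. That range is neither an estimate nor a bound. It counts PCyR as best response, so it misses patients with repeated PCyR assessments who later reach CCyR. It includes patients with no repeat assessment. It comes from second-line CP only, and imputation of CCyR from MMR (SAP 7) could change it. The number affected cannot be estimated from the documents.
- A reader might infer that every PCyR becomes a loss. A single PCyR with no later assessment is censored, and PCyR followed at the next visit by a maintained CCyR is not a loss.
- A reader might infer that the main results are affected. The primary MCyR rates do not use this rule, and the secondary durations of CCyR and MMR have loss rules that fit their own responses.

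Whether a fall from CCyR to PCyR is a loss of MCyR is a separate, open question. The progression list says yes, while Appendix 2 still counts PCyR as MCyR.

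**What to change.** In SAP 6.1, add an exception to the MCyR sentence and refer to it in SAP 8.2.3: for duration of MCyR, in a patient who has not yet attained CCyR on treatment, confirmed loss is two consecutive assessments at least 28 days apart with >35% Ph+ metaphases; progression, death and censoring are handled as for CCyR.

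Add a second sentence for patients who have attained CCyR, including after an initial PCyR, stating whether a confirmed fall to PCyR counts as loss of MCyR in this analysis. Reconcile that statement with the CP progression criteria in SAP 6.1 and Protocol 5.3, and with Appendix 2.

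The cost is two sentences in the SAP. The cut-off is already in Appendix 2 and the Ph+ percentages are already collected. No new data, protocol amendment or change to the clinical discontinuation criteria is proposed.
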